Visit 3 (Laboratory Session I) – Day 5 Participants will provide a urine sample (drug toxicology), and a one vial blood sample (β -endorphin, hormone levels). Participants will then complete a series of assessments (**Table 1**) and receive a single oral dose of yohimbine or yohimbine-matched placebo. Fifteen minutes later, participants will administer a dose of oxytocin or oxytocin-matched placebo (40 IU, 4 sprays per nostril), after 30 min the first sample of saliva (cortisol and oxytocin) will be collected and the cue-reactivity will begin (112). Cue-Reactivity (CR) Task will be administered in a similar manner to other published studies (72, 73) for individuals with OUD with cues selected based on patients' drug experience. To measure cue-induced opioid craving, participants will a view images of neutral stimuli and then of opioid drug use (24). Participants will rate their craving via drug visual analog scale (VAS) and the second sample of saliva cortisol will be collected (45 min later). Vital signs will be monitored during the entire procedure. Participants will then complete Post-Cue measures, will have their vital signs measured and conduct the last sample of saliva.

Visit 4 (Laboratory Session II) – Day 7 Participants will come back after two days. The procedure will be similar to Visit 3 but they will receive the opposite condition (yohimbine or yohimbine-matched placebo).

A two-day washout period will occur followed by initiation of the opposite intranasal medication condition (i.e. oxytocin and oxytocin-matched placebo) to be administered for one week starting at day 9.

Visit 5 (Laboratory Session III) – Day 14 Participants will complete the lab procedures as described in Visit 3 and 4, however, this time will be administered the opposite oxytocin condition (i.e. oxytocin or oxytocin-matched placebo). Participants will also receive yohimbine or yohimbine-matched placebo (counterbalanced).

Visit 6 (Laboratory Session IV) – Day 17 Participants will come back after two days. The procedures will be completed as described in Visits 3-5, but they will receive the opposite condition (yohimbine or yohimbine-matched placebo).

Visit 7 (follow-up) – Day 20 After three days, participants will come to the lab for the final assessments (Table 1).

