For those that have previously completed the study and will be re-enrolled in the opposite medication conditions, they will go through an additional two visits for safety criteria and to once again confirm eligibility: visit A and Visit B

Visit A: Participants will review their brief medical history questionnaire with the nurse practitioner, and compete assessments about any anxious or depressive symptoms.

Visit B: Upon completion of visits 5 and 6 where participants were randomized to the opposite medication condition, they will once again come to the lab to complete the final assessments **(Table 1)**.

Medication compliance: To ensure study medication compliance, oxytocin levels will be measured at screening (to determine oxytocin baseline values), at Visit 3, 4, 5 and 6. Buprenorphine levels will be checked by urine at each visit, in order to ensure ORT compliance and reduce the risk of withdrawal after study conclusion.

Assessments Demographic and baseline characteristics will be assessed according the CADRE standardized format (**Attachment B**). Additionally, specific for this project, we will include (**Attachment G**):

Opioid craving/withdrawal. a) Clinical Opiate Withdrawal Scale (COWS) (113) an 11-item scale that measures the stage or severity of opiate withdrawal and the level of physical dependence, b) Opioid Craving Scale (OCS) a 3-item scale adapted from the 3-item Cocaine Craving Scale (114), that assesses opioid craving and c) Opioid Timeline Follow-back (115) a calendar-assisted interview that will help participants estimate their amount of opioid use over the last 90 days.

Mood, Anxiety and Trauma Measures, in addition to the CADRE standardized assessments, we included anxiety and stress measure: a) Hamilton Anxiety Rating Scale (HAM-A) (116) is a 14-item scale that measures anxiety symptoms (psychic anxiety and somatic anxiety), b) Hamilton Rating Scale for Depression HAM-D a 21-item scale designed to assess potential depressive symptoms, and c) State-Trait Anxiety Inventory (STAI) (117) is 40-item measure that is split into state anxiety (20 items) and trait anxiety (20 items).

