The list of the CADRE standardized assessments and measures is attached (**Attachment B**) and *ad hoc* assessments administer during the study period is described in **Table 1** (**Attachment G**). Other potential effects of oxytocin as pharmacotherapy for OUD on relapse, drug-taking or subjective rating of drug effect will be monitored throughout the study.

TABLE 1 – Assessments						
Measure	Visit 1 Screening	Visit 2 Randomization	Visit 3, 4, 5 and 6 Laboratory	Visit 7 Follow-up	Visit A	Visit B
Adverse Events Evaluation (AEE)		x	x	x		X
Clinical Opiate Withdrawal Scale (COWS)	x	x	x	x	X	X
Concomitant medications, nicotine and marihuana use	x	x	x	x	X	x
Prior and Concomitant Medications Log	X	x	x	X	X	X
Hamilton anxiety rating scale (HAM-A)	x	x	х	x	X	X
Hormone blood collection (blood and saliva)	x		х			
Opioid Craving Scale (OCS)	x	x	x	x		X
State Anxiety Inventory-State (STAI-State)	x		х		X	
Trait Anxiety Inventory-Trait (STAI-Trait)	x					
Study medication accountability			x			
Buprenorphine urine level	x	x	x	x	X	X
Menopausal Health Questionnaire	x					
Hamilton Rating Scale for Depression HAMD	x				X	
PTSD PCL 5		x				
Drug Attention Scale (DAS)			x			

Desire for Drug Questionnaire (DDQ)		x	
Obsessive Compulsive Drug Use Scale (OCDUS)		x	
Drug or Treatment Drug Craving Questionnaire		x	

Clinical Laboratory Core (CLC)

Measures Aim 3 of the CADRE's Clinical Laboratory Core (CLC) is to build a center-wide database of transdiagnostic biological and environmental factors associated with the development and progression of SUDs and chronic disease. This database will enable CADRE project and pilot investigators to test multi-causal models of the relationships between SUDs and chronic disease. Measures to be included in all projects in service of this aim include: the MINI 7.0.2. (brief patient-completed structured clinical interview for DSM-5 disorders), measures of stigma, trauma, family history of alcohol/substance use, affective dysregulation (anhedonia), behavioral dysregulation (impulsivity), sleep, physical activity, health-related quality of life, and blood samples from which DNA will be extracted and biobanked for future analysis. All measures are described in the CLC Research Plan. The CLC measures will be included in each project's baseline assessment battery, along with project-specific measures, by the CLC's data management team to ensure uniformity in item wording and response format across projects.

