- Current substance disorder other than marijuana, nicotine and caffeine as assessed by self-report and urine toxicology screen at baseline;
- Current use of medications that may interact with study medications;
- History of hypersensitivity to study medications;
- Clinically significant electrolyte abnormalities, current rhinitis or use of vasoconstricting medications or prostaglandins.

NOTE: the exclusion criteria are based in reducing participants' safety.

Participants need to speak English and be able to understand informed consent and questionnaires in English which will be written exclusively at an 8th grade level.

One hundred individuals receiving buprenorphine/naloxone or methadone as opioid replacement therapy (ORT) will be screened, 80 will be randomized, with 50 expected to complete the study. Potentially eligible participants will be invited for an in-person screening, where they will provide written informed consent and undergo a physical examination in the NEW Clinical Laboratory Core (CLC).

The **sample size estimate** is based on recent findings reporting that baseline levels of stress significantly predicted oxytocin effects on cue-induced craving (Mitchell et al., *J Addict Med*, 2016). Effect sizes were calculated based on a between-subjects in oxytocin study with alcohol related responses (Pedersn et al., *ACER*, 2013). The estimate of opioid craving (measured by the OCQ) were calculated from the *M* and the *SD* of alcohol-related outcomes: oxytocin was superior to placebo in reducing alcohol withdrawal (*i.e.* less lorazepam required to complete detoxification: 3.4 mg±4.7, vs. 16.5 mg±4.4, p<0.01), lower mean CIWA scores (4.3 mg±2.3 vs. 11.8 mg±0.4, p<0.01). We estimated that with a standard threshold, α = 0.05, for med-large effect (f = 0.35), two group independent variable and three covariates in ANCOVA, the *N* is 67 to detect 0.80 power. With an additional 0.20 to account for attrition [N = 50 (completers) + 13 = 80 (enrolled)]. The estimated power at N = 67, with the addition of an interaction term (for Aim 2) would be = 0.63. Therefore, the calculated sample size is well powered to address the hypothesis of the main medication effect (Aim 1) and of the interaction effect with stress and anxiety (Aim 2).

5. Recruitment Methods

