Oxytocin, Stress, Craving, Opioid Use Disorder (OSCO)

STATISTICAL ANALYSIS PLAN

[name], PhD [name] [contact]; [contact] [contact]

ORIGINAL: 2019 AUGUST 08 REVISED: 2022 MAY 05

Clinical trial registration: Clinicaltrials.gov; NCT04051619

IND/FDA: 135570, oxytocin and yohimbine (Holder: [name])

Table of Contents

Study design, setting and approval	3
Statistical analysis	3
Missing data reporting	4
References	6

Study design, setting and approval

This was a Phase 1, outpatient, randomized, double-blind, cross-over (2x2 design with oxytocin and yohimbine), placebo-controlled, human laboratory study (**Figure 1**). The trial took place at the Center for Alcohol and Addiction Studies, Brown University, Providence, RI, USA from 2019-2023. The clinical protocol was approved by the Brown University Institutional Review Board (IRB), received an FDA Investigational New Drug (IND135570), and was registered on clinicaltrials.gov (NCT04051619). The study was initiated as a between-subjects design. However, following the COVID-19 pandemic, in order to speed up recruitment, the study was changed to a within-subjects crossover design. This modification in the clinical protocol was executed following the FDA Guidance Document on Changes or Modification during conduct of Clinical Investigations ¹. After receiving approval from the Brown University IRB in November 2021, the FDA was notified in an annual progress report and the study design was updated on clinicaltrials.gov in February 2022.

Statistical analysis

For all outcomes, we utilized an intention-to-treat (ITT) approach, where participants were examined based on their *a priori* randomized protocol and received at least one dose of the study medication (oxytocin or oxytocin-matched placebo)²

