Outcomes: Primary (craving) and secondary (safety and tolerability) outcomes were assessed in realtime in the laboratory. Seven-day oxytocin administration was compared to the oxytocin-matched placebo condition during the CR procedure, in which noradrenergic activation produced by yohimbine or yohimbinematched placebo condition (2X2 design) was measured. We used Generalized Linear Model (GLM) with modelbased estimator in the covariance matrix, with medication (oxytocin/placebo) and noradrenergic activation (yohimbine/placebo) as within-subject factors. The model was specified to evaluate the effect of drug (oxytocin/placebo) by noradrenergic (vohimbine/placebo) interaction, main effect of the drug, and main effect of noradrenergic activation. Craving was assessed using the DDQ with time coded as: t_0 =relaxation, t_1 =interaction with drug paraphernalia/opioid auditory cues and t_2 =opioid use video. Safety and tolerability were assessed using: SBP, DBP, HR (vital signs), HAM-A and STAI (anxiety). The STAI y1 (state) was included as an additional safety measure for anxiety to ensure participants were not experiencing acute symptoms of anxiety within the laboratory. The STAI y2 (trait) was inserted as a covariate in the model to control for baseline anxiety level, along with stress (PSS), HPA (cortisol), and noradrenergic response (α -amylase). Time at laboratory sessions was coded as: t_0 =baseline, t_{45min} =45-min after yohimbine administration, and t_{90min} =post cue-exposure to specifically evaluate the contribution of each laboratory procedure (vohimbine and CR). Withdrawal symptoms (COWS) and AEs were assessed at specific timepoints: t_0 =pre-laboratory and t_1 =post-laboratory procedures.

Other outcomes (safety and tolerability) were measured retrospectively during the one-week outpatient setting and included the: COWS (withdrawal), anxiety (HAM-A and STAI), stress (PSS), depression (HAM-D) and AEs. The other outcomes were analyzed using ANOVA test and the number of AEs via a χ^2 test. For missing data approach, we first categorized missing data as missing completely at random (MCAR), missing at random (MAR) or missing not at random (MNAR)⁷. Analysis with GLM (using all available pairs of data to model missing values with maximum likelihood estimation) was deemed suitable for our analyses because no systematic differences existed between participants with missing data and those with complete data (MCAR)⁸.

Missing data reporting ⁹

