- 1. Amount of missing data in the dataset:
 - a. Oxytocin condition: 10% did not receive either oxytocin or placebo condition (within subject, *n*=16; between subject, *n*=4)
 - b. Yohimbine condition: 11.12% did not receive yohimbine condition (yohimbine, *n*=14; placebo, *n*=16; no yohimbine, *n*=4):

- 2. Reason for missing:
 - a. Oxytocin condition: change from between subject to within subject design
 - b. Yohimbine condition: safety concerns due to past history of cardiovascular disease and/or current hypertension (*n*=3), stroke (*n*=1)

3. Consequences:

- a. *Oxytocin condition*: no differences between participants with and without missing values except there were no subject taking methadone in the subjects with missing values.
- b. *Yohimbine condition*: no differences between participants with and without missing values except there were cardiovascular concerns in the subjects with missing values.
- 4. *Method*: GLM with MNAR using all available pairs of data to model missing values with maximum likelihood estimation
- 5. Software: IBM SPSS Statistics for Windows, version 29 (IBM Corp., Armonk, NY, USA)

All statistical analyses were performed after participants had completed their follow-up visits and the study database had been locked. The results were presented using summary statistics: number of subjects (n); mean (M); standard deviation (SD) or frequency distributions (%) and effect size was reported as Cohen's d.

All statistical procedures were performed by IBM SPSS Statistics for Windows, version 29 (IBM Corp., Armonk, NY, USA), and GraphPad Prism (v.10) was used to generate figures (La Jolla, CA, USA). All statistical tests were two-tailed, and statistical significance was accepted if an alpha value p<.05 was obtained.

References

1. FDA. Changes or modifications during the conduct of a clinical investigation; final guidance for industry and CDRH staff. 20012001.

Schulz K, Altman D, Moher D. Consolidated Standards of Reporting Trials Group CONSORT
2010 Statement: Updated Guidelines for Reporting Parallel Group Randomised Trials. Bmj.
2010;340:c332.

4. Tukey JW. The future of data analysis. The annals of mathematical statistics. 1962;33(1):1-67.

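### The protocol names no primary craving scale, and the only SAP text that settles on the DDQ was written with data in hand, so the DDQ cannot be shown to be prespecified

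*Protocol*

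**What the plan says.** **Protocol.** Aims 1 and 2 concern cue-induced opioid craving, but no scale is designated primary.

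- Part III, section 3, Visit 3 (Laboratory Session I), describing the cue task: "Participants will rate their craving via drug visual analog scale (VAS".
- Assessments paragraph: "Opioid Craving Scale (OCS) a 3-item scale". Neither the VAS nor the DDQ is described there.
- Table 1: rows for the OCS, "Desire for Drug Questionnaire (DDQ"), the OCDUS and a drug craving questionnaire. The VAS has no row.
- Section 4, sample-size paragraph: "The estimate of opioid craving (measured by the OCQ) were calculated". The OCQ appears nowhere else under that name.

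**SAP.** The Outcomes paragraph calls craving primary and states: "Craving was assessed using the DDQ with time coded as" three points, from relaxation to an opioid-use video. The VAS is not mentioned and no reason for using the DDQ is given. The paragraph just before, on sample size, attaches the word primary to safety and tolerability.

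**SAP timing.** The title page reads "ORIGINAL: 2019 AUGUST 08 REVISED: 2022 MAY 05". The design section, in the past tense, places the trial at "Brown University, Providence, RI, USA from 2019-2023". The Statistical analysis section reports five cortisol outliers as already Winsorized. Missing data reporting gives participant counts by condition and compares people with and without missing values. It closes: "All statistical analyses were performed after participants had completed their follow-up visits and the study database had been locked".

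**The concern.** A p<.05 on craving keeps its nominal error rate only if the scale was fixed before anyone could see results. The protocol leaves several candidates open, so the SAP has to carry the prespecification. The SAP in hand cannot do so, because its wording is later than its stated date and later than lock.

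At stake is how the craving result may be described. If no dated earlier record names the DDQ, a reader cannot tell a planned test from the most favourable of several. The conflict over whether safety or craving is primary makes this worse, since it leaves open which result the trial stands on.

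**Working it through.** **1. The plan's own figure.** The sample-size paragraph gives N = 67 for 0.80 power (f = 0.35, two groups, three covariates, α = 0.05).

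- Noncentral F: λ = f²N = 0.35² × 67 = 8.21; df1 = 1; df2 = 67 − 2 − 3 = 62. Power is 0.805, and 67 is the smallest N that reaches 0.80.
- With df1 = 3, power at N = 67 is 0.636, against the stated 0.63 with the interaction term.

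Both reproduce. Neither fixes the instrument: the paragraph derives its estimate from alcohol-withdrawal outcomes, not from data on any of the craving scales.

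**2. Which scales are in play.**

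| Place | Scale |
|---|---|
| Protocol, Visit 3 cue task | VAS |
| Protocol, sample size | OCQ |
| Protocol, Table 1 | OCS, DDQ, OCDUS, drug craving questionnaire |
| SAP, Outcomes | DDQ |

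Two scales are tied to the cue task: the VAS (protocol) and the DDQ (SAP). Five are named for the laboratory visits: VAS, OCS, DDQ, OCDUS and the drug craving questionnaire. Table 1 is broken in extraction, so placing the single mark for the DDQ, OCDUS and questionnaire in the laboratory column is the likely reading, not a certain one. The OCQ is left out of the count because it may be another name for a listed scale.

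**3. Can the SAP text date from May 2022?** A plan written then could have foreseen an end in 2023. It could not have reported in the past tense that the trial took place through 2023, that final missingness had been counted, or that analyses had followed completed follow-up and lock. The current text was therefore written after the revision date it carries, and after lock.

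**4. What free choice of scale would cost.** For k independent two-sided tests at 0.05, the chance of at least one p<.05 under the null is 1 − 0.95^k.

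- k = 2: 1 − 0.95² = 0.0975
- k = 5: 1 − 0.95⁵ = 0.226

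Scales measured in the same people are correlated. The documents give no correlations, so a range was assumed and k equicorrelated z-statistics were simulated (400,000 draws each):

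| Correlation | 0 (exact) | 0.3 | 0.5 | 0.7 | 0.9 |
|---|---|---|---|---|---|
| k = 2 | 0.098 | 0.094 | 0.090 | 0.083 | 0.071 |
| k = 5 | 0.226 | 0.209 | 0.182 | 0.148 | 0.101 |

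These count a result in either direction and only the choice of scale. The SAP also names no DDQ score and no single contrast across its three time points. That freedom is not in the figures.

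**The case against.** A reader might infer that the primary outcome was switched from the VAS to the DDQ after results were seen. The documents do not support that, for three reasons.

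- The protocol never labels the VAS, or any craving scale, primary. The DDQ is in its Table 1, so it was a planned measure and not a later addition.
- Late wording does not date the decision. The August 2019 SAP, or a genuine May 2022 version, may already have named the DDQ; neither is available here. The data-derived items in the current text concern cortisol and missing conditions, not the craving scale.
- The false-positive figures describe unrestricted choice of the smallest p-value, and nothing shows that this occurred. Zero correlation is also an extreme case for craving scales in the same participants, so the upper ends are bounds.

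Two further points carry weight. The VAS is mentioned only in the Visit 3 text, with no Table 1 row and no SAP entry, so separate VAS data may not exist. The SAP also presents the study as Phase 1 and preliminary, which lowers the stakes of one p-value.

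All of this narrows the point without removing it. Being one of several listed scales is not prespecification as primary, and the date conflict is internal to the SAP. Running analyses after lock is proper practice; the difficulty is a plan that reports them as done while carrying an earlier date.

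**Conclusion.** The point holds in limited form. The protocol leaves the primary craving scale open, and the VAS, OCQ and DDQ are not reconciled. The SAP contradicts itself on which outcome is primary, and its content is later than its latest date. On these documents the DDQ result cannot be presented as prespecified. That is a gap in the evidence and not a finding that the scale was selected on results.

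If choice had been free, the nominal 5% would become about 7-10% for the two cue-task scales and about 10-23% for the five laboratory-visit scales. These ranges rest on assumed correlations from 0.9 down to 0, equal between scales, and on picking any significant result. A dated pre-unblinding version naming the DDQ as the primary craving measure would settle the scale question; the SAP's date and its conflict over the primary outcome would still need correcting.

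**What to change.** 1. Correct the SAP date to that of the current text.
2. State once whether craving or safety is primary, and remove the conflicting label.
3. Cite the dated pre-unblinding version that names the DDQ. If none exists, label the choice of the DDQ post hoc and the craving result exploratory.
4. Establish whether VAS ratings were collected. If so, report the same oxytocin-versus-placebo contrast on the VAS beside the DDQ. If not, say that the VAS was not collected.

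The cost is SAP wording and at most one extra analysis of data already held. The real downside is that the craving claim may become exploratory.

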This study will use a within subject design with oxytocin vs. oxytocin-matching placebo and yohimbine vs. yohimbine-matching placebo. The cue reactivity (CR) (opioid craving induced by personalized opioid cues) will follow the physiological symptoms (triggered by yohimbine) to isolate the stress signal associated with opioid. Eligible participants will be randomized to use intranasal oxytocin or placebo spray under double-blind conditions for 7 days. On days 5 and 7, participants will complete a session in which they receive yohimbine and one in which they receive placebo, under double-blind conditions, with the order of these conditions randomized across participants. After a two-day wash-out period, participants will receive the opposite condition within the oxytocin group (oxytocin or placebo, counterbalanced) to be administered for 7 days. On days 14 and 16, participants will complete an additional two labs where they will receive yohimbine and yohimbine matched placebo (counterbalanced). In a follow-up visit, we will complete final assessments before concluding the study (**Figure 1**).

FIGURE 1 - Pharmacological interventions during the study

Drugs and Doses Participants will receive intranasal oxytocin (40 IU) and oxytocin-matched placebo twice a day for 14 days; there will be one week of oxytocin administration and one week of placebo administration with two days of washout between the two conditions. They will receive two oral doses of yohimbine (32.4 mg) and two oral doses of yohimbine-matched placebo in the laboratory sessions.

[name] already obtained the Investigational New Drug (IND: 135570) from FDA for this study (Appendix A).

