The ITT analysis was suitable for this crossover design ³ as the placebo condition was treated identically to the active drug condition (route, administration and laboratory procedures). Distributional characteristics of outcome measures were examined to evaluate similarity to the normal distribution. detailed descriptive analysis of demographics, substance use, and clinical characteristics. The cortisol had a kurtosis in excess of four; consequently, an outlier analysis was performed and a total of 5 outliers falling outside of ±3 interguartile range were Winsorized as recommended ⁴. Comparisons with these characteristics, in relation to enrolled versus completer status, were performed using *t*-tests to analyze continuous variables (age) and χ^2 for categorical variables (sex, race, medication status). Attrition rates between the screening visit and follow-up visit were examined descriptively to assess for potential bias. In addition, a logistic regression was performed to test for possible bias due to period (placebo first, then oxytocin and oxytocin first, then placebo) or medication carryover (placebo and oxytocin), as done in our prior cross-over trial ⁵. This study tested the feasibility of the combined study design, the safety and tolerability of IN oxytocin and yohimbine, and the potential value of testing IN oxytocin as adjunct therapy in an appropriately-powered larger RCT. In selecting a target sample size, we balanced power considerations and feasibility given the preliminary nature of this trial. Because of the within-subjects design, power to test the effects of the study drug was optimized for this modest sample size. For the safety and tolerability outcomes (primary) adverse events, difference was detected based on a

judgement concerning the minimal effect, which has clinical relevance in the management of patients. In a noninferiority trial, the exact sample size could not be fixed in advance because it depends upon the chosen stopping guidelines ⁶.

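### The crossover model has no period term, and the separate logistic check for period does not adjust the oxytocin contrasts

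*Protocol*

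**What the plan says.** **Design history.** The SAP (Study design, setting and approval) states: "The study was initiated as a between-subjects design". The switch to a within-subjects crossover is dated "After receiving approval from the Brown University IRB in November 2021", in a trial that ran from 2019 to 2023.

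**Concurrent crossover.** Protocol Part III, section 3: "After a two-day wash-out period, participants will receive the opposite condition within the oxytocin group". Corresponding laboratory sessions fall on days 5 and 14, nine days apart.

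**Re-enrolment.** The same section adds Visits A and B "For those that have previously completed the study and will be re-enrolled in the opposite medication conditions". It gives no minimum or maximum interval. For Visits 5 and 6 it uses the words "where participants were randomized to the opposite medication condition", although an opposite condition is fixed by the first one.

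**Outcome model.** The SAP's Outcomes paragraph fits the model "with medication (oxytocin/placebo) and noradrenergic activation (yohimbine/placebo) as within-subject factors", with their interaction and with trait anxiety, perceived stress, cortisol and α-amylase as covariates. It names no period, sequence, enrolment-route or calendar-time term.

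**Period check.** SAP, Statistical analysis: "a logistic regression was performed to test for possible bias due to period" or medication carryover. Period is defined there by the order of the two conditions.

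**Numbers.** SAP, Missing data reporting: 16 within-subject and 4 between-subject participants, in one dataset.

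**The concern.** In a two-period crossover, anything that changes between the first and second week (familiarity with the cues, time in treatment, outside events) moves the second-period scores. A period term takes that movement out of the drug contrast. Without it, protection comes only from equal sequence sizes, and the shift still enters the error variance.

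The point matters more than usual here because the second period may not mean the same thing for everyone. For concurrent participants it starts two days after the first condition ends. For anyone re-enrolled it starts after an unstated interval.

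At stake are the oxytocin main effect and the oxytocin–placebo contrast after yohimbine (Aim 1), for craving and for the safety measures in the same model. The oxytocin-by-yohimbine interaction is less exposed. Both yohimbine conditions occur within each period, so a shift that affects both sessions equally cancels in the difference of differences.

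**Working it through.** **Number of pairs.** The SAP's 10% missing share reproduces: 20 participants × 2 oxytocin conditions = 40 cells, 4 of them empty, and 4/40 = 10%. That is consistent with 16 pairs. The documents give no figure for period effects, so the rest depends on assumed values.

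**Bias without a period term.** Let d be one person's oxytocin-minus-placebo difference, τ the true effect and δ the period-2-minus-period-1 shift. Then d = τ + δ if oxytocin came second (PO), and d = τ − δ if it came first (OP). Averaging over n pairs:

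bias = δ × (n_PO − n_OP)/n

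With n = 16: 8:8 gives 0; 10:6 gives 4/16 = 0.25δ; 11:5 gives 6/16 = 0.375δ; 12:4 gives 8/16 = 0.50δ. If δ is 0.5 SD of the within-person difference, the bias is 0.125 SD at 10:6 and 0.25 SD at 12:4.

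**Error variance.** The omitted shift also inflates the variance of d. Taking the variance without a shift as 1, its expected value becomes 1 + δ²[1 − ((n_PO − n_OP)/n)²] × n/(n − 1). At 8:8 with δ = 0.5 this is 1 + 0.25 × 16/15 = 1.27, so the standard error is about 13% too large. Hence the conservative test.

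**Type I error.** Two-sided 5% test, 40,000 simulated trials of 16 pairs, with a paired t-test standing in for the SAP model:

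| Split | δ = 0.25 SD | δ = 0.5 SD | δ = 1 SD | With period term | SE multiplier |
|---|---|---|---|---|---|
| 8:8 | 4.4% | 2.8% | 0.7% | about 5% | 1.00 |
| 10:6 | 5.0% | 4.7% | 3.5% | about 5% | 1.03 |
| 11:5 | 5.5% | 7.6% | 9.9% | about 5% | 1.08 |
| 12:4 | 6.8% | 11.6% | 22.9% | about 5% | 1.15 |

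The multiplier is √[(1/n_PO + 1/n_OP)/4] ÷ √(1/n). At 12:4 this is √(0.333/4) ÷ 0.25 = 1.15. It compares standard errors at the same residual SD. A period term also removes the shift from the residual, which offsets part of this cost.

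**Shift in re-enrolled participants only.** If a of them had oxytocin second and b had it first, the unadjusted bias is δ(a − b)/16. With a period term it is (δ/2)(a/n_PO − b/n_OP). For an assumed 8:8 trial with a = 6 and b = 2, both give 0.25δ: 4/16 in the first formula, and ½ × (6/8 − 2/8) in the second. A plain period term does not repair this case, so it needs separate handling by route.

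**Do other elements of the plan stand in for period?**
- *Logistic check.* Its binary outcome is not named, its period is really sequence, it ignores interval and route, and it has little power with 16 pairs. Whatever its result, it leaves the craving and safety estimates unchanged.
- *Covariates.* None indexes period. Protocol Table 1 schedules trait anxiety only at Visit 1, so it cannot follow change up to a second enrolment.
- *Visit A.* Table 1 does not schedule the Opioid Craving Scale there, so re-entry has no scheduled craving measure before the second condition.

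**Limit of the calculation.** The formulas cover 16 complete pairs. The SAP model also uses the 4 unpaired participants, whose between-person information would alter the weights somewhat.

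**The case against.** The strongest reply is that order was randomized or counterbalanced, so the unadjusted contrast has no systematic bias unless completing or returning depended on sequence, and nothing in the documents shows that it did. Severe imbalance is also uncommon. Under simple 1:1 allocation of 16 (an assumption), a split of 12:4 or worse arises 7.7% of the time, against 45% for 10:6 or worse, and at 10:6 the type I error is not inflated. This stands and limits the size of the concern. It does not make omission harmless. At 10:6 the estimate still carries a quarter of the shift, with the inflated variance hiding it from the test, and at 8:8 power is lost.

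Re-entry is also screened. Visit A reconfirms eligibility and repeats withdrawal, anxiety, depression, medication and urine buprenorphine checks, and a stable replacement dose for at least 3 months is an inclusion criterion. That limits recent instability but not every change between periods. Habituation to cues could occur on either route, which supports a period term in general rather than a concern about re-enrolment alone.

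Finally, a route-by-period term is barely estimable with 20 participants. This is right, and it is why that term belongs in a sensitivity analysis.

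A reader might infer that earlier completers were in fact brought back and pooled across a gap running from 2019 to after November 2021. The documents do not say so. The protocol text is prospective, the SAP never mentions re-enrolment, and any number of the 16, including none, may have come by that route. The dates give only an outer limit. Nor does either document report a correlation, so a different within-person correlation in long-gap pairs cannot be asserted.

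**Conclusion.** The point holds in a conditional form. The craving and safety model for a crossover has no period term, and the separate logistic regression does not supply the adjustment. The possible consequence is 25% of any common period shift in the oxytocin contrast at 10:6 and 50% at 12:4. At 8:8 the bias is zero, but the test is conservative (2.8% instead of 5% for a 0.5 SD shift).

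The split, the number re-enrolled, their interval and the shift are all assumptions. It would be too strong to conclude that the oxytocin estimate is biased: the documents show neither an imbalance nor a shift. They show that the analysis is not protected against the combination, and that the reader lacks the counts needed to rule it out.

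**What to change.** - Add period (first or second intranasal condition) as a fixed effect to the craving and safety models. Keep the logistic regression as a descriptive check only.
- Tabulate sequence (placebo first, oxytocin first) by enrolment route (concurrent, re-enrolled), with the interval between conditions.
- If anyone was re-enrolled, add a labelled sensitivity analysis that excludes their second period, or adds route-by-period where numbers allow.

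The SAP describes the analyses as already performed after database lock, so this is a wording change and a re-run on existing data, and the report should say that the term was added.

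The cost of the period term is one degree of freedom (15 to 14 in the paired version) and, at the same residual SD, a standard error unchanged at 8:8, about 3% larger at 10:6 and about 15% larger at 12:4. The sensitivity analysis will be imprecise and should be read for direction rather than significance.
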